Psychological First Aid for Injured Kids

1.4 *Provide a short summary of the purpose and procedures of the study proposed in this IRB application.*

- **DO NOT include information on studies not proposed in this application.**
- **Use LAY terminology only. This must be easily understandable by IRB community members and nonscientists.**
- **DO NOT cut and paste technical abstracts from funding applications that may not be understood by a general audience.**

Phase 1

We propose to conduct eight focus groups: two composed of approximately 6-10 parents each at University of Iowa Children's Hospital and two composed of approximately 6-10 parents at Blank Children's Hospital. We will also conduct two of approximately 6-10 pediatric health care providers each from the University of Iowa Children's Hospital and two of approximately 6-10 pediatric health care providers each from Blank Children's Hospital. The purpose of the parent focus groups is to establish the parent's willingness to participate in a study to reduce the psychological effects of injury on their children, and a parent's acceptability of the LPC for Injured Kids materials. The purpose of the pediatric health care provider focus groups is to understand the types of trauma experienced by children, the psychosocial consequences encountered by traumatized children and the types of services perceived as available, accessible, and acceptable to families particularly from rural Iowa. In addition, providers will be asked to provide feedback on the LPC for Injured Kids materials. If a health care provider is unable to participate in the focus group but wishes to be interviewed individually, the purpose and the questions asked during the interview will be identical to those of the focus group. Each focus group/interview is expected to last between 60 and 90 minutes.

Phase 2

Children between 10-17 years of age presenting to the UIHC and Blank Children's Hospital with an unintentional injury requiring admission will be the sample population. Blank Children's Hospital has submitted a separate IRB for their participation in the study. A child will be included if they are 10-17 years old with an unintentional injury. Consenting children and their parents will be asked to complete a series of four questionnaires: before hospital discharge, at 6 weeks post discharge, 3-months and 6-months post discharge. The parent-child dyads will be randomized (1:1) to receive training in Link for Injured Kids or to receive Trauma Education (parent booklet, "So, you've been in an Accident"). The survey completed in the hospital will be a paper survey or online via iPads, and follow-up surveys can be completed on paper or online.

1.5 *Specify your research question(s), study aims or hypotheses (do not indicate "see protocol")*

Phase 1

Assess the feasibility of LPC for Injured Kids through qualitative research with parents of previously injured children and social workers and pediatric trauma providers from the UI Children's Hospital and Blank Children's Hospital. The focus group findings will also help inform and refine intervention materials and delivery.

Phase 2

Through a randomized trial, determine the range of potential psychosocial and behavioral health indicators possibly impacted by Link for Injured Kids. This will identify the types of outcomes which could include PTSD, depression, nonspecific distress, quality of life, absenteeism, school performance, coping skills, communication skills, and access to mental health.

1.6 *Background and significance and/or Preliminary studies related to this project. (do not indicate "see protocol")*

According to the Centers for Disease Control and Prevention, the number one cause of death and morbidity among children ages 1-19 is unintentional injury. Each year, approximately 12,000 children die from unintentional injury causes (1). Of all injury causes, motor vehicle crash leads to the most number of deaths to children in U.S. as passengers, teen drivers and pedestrians. Almost 400,000 injured teen drivers and occupants were seen in emergency departments in the US in 2005 (2). In the U.S., falls lead to the highest number of childhood injury emergency department visits followed by injuries due to being struck by or against an object (1). Fire or burns are also an important cause of injury as the second leading cause of injury death to children between 1 and 19 (1).

Unintentional injuries, particularly severe injuries that impact daily functioning, can have longlasting psychological effects. Prevalence of posttraumatic stress symptoms is estimated at 29% during the first month post-trauma and 13% between 3-6 months post-trauma. (3)

Within 12 months of being hospitalized because of injury, 19-32% of adolescents developed PTSD. (4) A variety of injury experiences can lead to PTSD symptoms including traffic crashes, burns, falls and animal attacks. (5) Adolescents involved in a mass burn incident had significantly more mental problems than community controls one year after the incident (6), and, 12% of schoolchildren exposed to an industrial fire met the criteria for PTSD. (7) Approximately 30% of pediatric pedestrian injury cases have acute stress disorder or PTSD. (8-10) Many cases of psychological trauma are missed in hospital settings and sent home. This proposed project will empower families with skills to identify trauma-induced mental health distress and resources for referral to advanced mental health care.

Our innovative project addresses the need for evidence-based practices to improve the acute care of children post-injury. Psychological First Aid (PFA), analogous to physical first aid (11), “uses interpersonal skills provided by individuals to respond to psychological consequences of [trauma] in their own lives, as well as in the lives of their family, friends, and neighbors (p. 4–5)” (11). Informed by previous research on posttraumatic risk and resilience, PFA provides information, education, comfort and support through human contact in order to accelerate recovery and promotion of mental health (12, 13).

In 2006, psychologists developed a child-focused version of PFA in school and community settings called “Listen, Protect, Connect (LPC)-Model and Teach.” LPC outlines steps for administering PFA to children after any type of crises, either a large-scale disaster or local emergency. The effectiveness of PFA has not been scientifically evaluated. We propose to create an adapted version of LPC for families. LPC has the potential to be a national tool that possibly improves coping, access to mental health care, and acute PTSD symptoms for children impacted by both individual and community emergencies (see Approach for description of LPC).

Preliminary Studies

[name] (PI) has over ten years of experience conducting pediatric injury, violence and disaster preparedness research, including studies of school-related injuries to children with disabilities (14-16); high school sports injuries (17); and emergency preparedness among staff, students and parents (18-20). Recently, [name] began studies focused on the psychological trauma in school settings. Studies of Psychological First Aids. In July 2008, [name] conducted studies of Listen Connect Protect (LPC) in the school setting, a precursor to the work proposed here. In the first study, 200 randomly selected flood-affected children were invited to participate, but only 8 enrolled into the study. In the second study, students seen at or referred to school nurses’ offices potentially impacted by various types of trauma (e.g., unintentional injury, violence, the floods) were enrolled. In total, 20 students were treated with LPC and followed-up.

The LPC intervention had high fidelity and acceptance among clients and nurse providers. Specifically, 90% of sessions followed the Listen Steps, 85% the Protect Steps, and 75% the Connect Steps. Feedback from subjects and nurse providers was also extremely positive, with 80% of children reporting feeling comfortable speaking with the school nurse, and 60% of students indicating that the LPC sessions were helpful in dealing with recent life events. One student with elevated scores of distress on the K6 screening tool (PTSD screener included in the LPC repertoire) was immediately referred to advanced mental health care. Human subject protection approval for LPC has already been obtained, and protocols were developed and tested. The new project will adapt materials from this school-based study and apply the intervention to families of injured children seen at the UIHC.

Flood-induced stress among college students. In August 2008, [name] conducted a university-wide survey to measure disaster health impacts of the Great Flood of Iowa among University of Iowa students. Of the 10,500 summer enrolled students, 1,404 responded. Eight percent of students had symptoms consistent with PTSD. The most commonly reported symptom was feeling emotionally upset (12%). Another 7% reported frequent trouble sleeping and 6% reported frequent trouble concentrating. About 7% of students reported increased drug and/or alcohol use following the floods.

“So you’ve been in an accident,” the second early intervention strategy to be tested in the proposed study, takes into account the challenges of hectic hospital settings and busy families. Given time and other constraints, educational materials may be a simple, cost-effective early intervention option when nothing else is available. [name] (Co-I of this research project) tested his materials at two children’s hospitals in Queensland. In the intervention hospital, pediatric trauma patients (11-17 years old) and their parents received booklets within 72 hours of admission, while control patients and parents at the other hospital received no materials. Over the follow-up period, children in the intervention hospital had significantly lower levels of stress. Their parents also showed promising outcomes such as fewer intrusive post-traumatic stress symptoms than control group parents. In their implementation evaluation of the materials, 97% of parents and 83% of children in the intervention arm reported reading them, and of those, 72% of parents perceived the booklets as having a positive effect on them and 57% thought the materials benefitted their children (18,19).

1.7

Literature cited / references (if attaching a grant or protocol enter N/A).

2. CoI, Violence and Poison Prevention: American Academy of Pediatrics. Policy statement-Pedestrian safety. *Pediatrics* 2009;124(2):802-12.

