VII.E.2 *Describe randomization scheme/assignment including ratio such as 1:1, 2:1 etc.*

Phase 1: No randomization

Phase 2

The parent-child dyad will be randomized at a 1:1 ratio by a program developed in Microsoft Access or Excel.

VII.E.3 *Will any questionnaires, surveys, or written assessments be used to obtain data directly from subjects in this study?*

Yes

VII.E.4 *List all questionnaires, surveys, written assessments and ATTACH each one to the application. (NOTE: You are NOT prohibited from attaching copyrighted materials to this application)*

Phase 1

Two focus group questionnaires have been developed: a questionnaire for parents of injured children and a questionnaire for staff who serve these injured children. The questions for the parent interview will be equivalent to the parent focus group questions. The questions for provider key informant interviews will equivalent to those of the provider focus group. At each focus group, one study staff member will ask the questions and a second person will take notes on the answers from the participants. In the telephone interview, notes will be taken by the research staff member completing the telephone interview

Phase 2

The parent and child will be asked to answer 4 questionnaires each over the course of the study: one during hospitalization, one at 6-weeks, one at 3-months and one at 6-months post hospitalization. The 6-week, 3-month and 6-month questionnaires will be the same questionnaire.

Both parent and child will complete the baseline questionnaire and follow-up questionnaire three times.

The parent and the child questionnaires will contain the following validated questionnaires: Strengths and Difficulties Questionnaire; the Pediatric Quality of Life Inventory; CESD; Foa PTSD; Multidimensional scale of perceived social support; open family communication; and how I cope under pressure.

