Staff who are experienced in conducting focus groups will be used in this project. If a focus group participant become visibly upset during the session, they will be referred to [name], Pediatric Psychology, UI Children's Hospital.

In the parent focus group, participation in the focus group may risk a loss of confidentiality although parents will only be asked to use their first name or a pseudo name during group introductions.

In the provider focus group, providers will be asked to remove their UIHC/ Blank Children's Hospital badges to reduce the risk of loss of confidentiality. Only the research team will receive the RSVP's through the doodle link or email to ensure confidentiality.

Phase 2

All parent-child dyads recruited at UIHC will be provided contact information for [name] and the UIHC pediatric psychiatry clinic should either experience an emotional/psychological issue requiring further attention. All parent-child dyads recruited at Children's Mercy Hospital will be provided with contact information for a general social work hersupport should with either experience an emotional/psychological issues requiring further attention.

Medical record abstraction data will be recorded by study subject identification number to reduce the likelihood of breach of confidentiality.

As mandatory reporters, the discovery of child abuse by a research team member will result in an immediate report to the University of Iowa Police and local police, consistent with Iowa Code 262.9(37).

VIII.3

Does this study have a plan to have an individual or committee review combined data from all subjects on a periodic basis (such as summary or aggregate safety and/or efficacy data)?

No

IX. Benefits

IX.1

What are the direct benefits to the subject (do not include compensation or hypothesized results)?

Participants may not benefit from being in this study.

IX.2 *What are the potential benefits to society in terms of knowledge to be gained as a result of this project?*

Phase 1

Parents of children with a traumatic unintentional injury, the children themselves, and health care providers of these injured children may potentially benefit from the development of this new program to reduce psychological trauma following an unintentional injury.

Phase 2

Parents of children with a traumatic unintentional injury and the children themselves may potentially benefit from these programs to reduce psychological trauma following an unintentional injury.

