The focus group data and key informant interviews will be analyzed using content analysis and identification of themes. Focus group and interview data will also be used to incorporate changes into the LPC for Injured Kids program.

Phase 2

If we achieve randomization, we will compare the differences in distributions between intervention and control groups using simple chi-square tests for categorical outcomes (low, medium, high levels of coing; being symptomatic for PTSD, Depression, etc.) and t-tests or Wilcoxon rank-sum tests for continuous variables depending on their normality (e.g. scores for PTSD, depression, social support).

If we do not achieve randomization (i.e. distribution of demographics are not balanced across intervention and control arms), we will also adjust for confounding using Generalized Linear Models and appropriate link functions (logit for binary outcomes, linear for continuous outcomes).

XI.2 *Provide the rationale or power analysis to support the number of subjects proposed to complete this study.***Phase 1**

The research team needs each final focus group to contain at least 6 parents or providers to get an adequate response to the focus group questions. The focus group will have potentially unpredictable schedule, either due to children in the home (parents) or heavy work load (providers) therefore we are recruiting 10 members per focus group to ensure we have at least 6 attending each focus group.

Phase 2

We conducted sample size based on testing a moderate effect size of 0.5 standard deviation comparing Trauma Education vs Link. With an alpha of 0.05, a sample size of 134 parent-child dyads in each of the arms (n=268) has 100% power to examine comparisons. We will oversample by 12% for a total n = 300.

XII. Future Research

XII.1 *Do you wish to keep any information about subjects involved with this research project so that members of the current research team may contact them in the future for your own research projects?*

No

XII.2 *Do you wish to keep any information about subjects involved with this research project so that [other researchers](#) may contact them for future research?*

No

XII.4 *Does this project involve storing any data, tissues or specimens for future research?*

No

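### No primary outcome, respondent or follow-up is named, and the 100% power in XI.2 is 98% for one continuous score and does not carry over to the planned comparisons of symptomatic status

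*Protocol*

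**What the plan says.** Section 1.5, Phase 2, sets the aim to "determine the range of potential psychosocial and behavioral health indicators possibly impacted by Link for Injured Kids". It goes on to name nine types of outcome that might be included: PTSD, depression, nonspecific distress, quality of life, absenteeism, school performance, coping, communication, and access to mental health. None is ranked.

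Section VII.E.4 says: "The parent and the child questionnaires will contain the following validated questionnaires", and lists seven scales. Each parent and each child completes them at baseline and three times afterwards: "The 6-week, 3-month and 6-month questionnaires will be the same questionnaire". Neither respondent and none of the three follow-ups is marked as the main one.

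Section XI.1 plans chi-square tests for categorical outcomes, with the example "being symptomatic for PTSD, Depression, etc", and t-tests or Wilcoxon tests for continuous variables, with the example "scores for PTSD, depression, social support". PTSD and depression therefore appear in both forms.

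Section XI.2 gives one calculation: a difference of 0.5 SD between Trauma Education and Link, alpha 0.05, and the conclusion that "a sample size of 134 parent-child dyads in each of the arms (n=268) has 100% power to examine comparisons". Enrolment is then raised by 12% to 300.

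**The concern.** A power statement means something only for a stated comparison. XI.2 does not say which scale, whose report, which visit, or whether the score or the symptomatic status is compared, and nothing elsewhere in the protocol fills the gap. Naming the primary outcome is normally the protocol's job, so it cannot simply be assumed to sit in the SAP.

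Two things are at stake. First, this document fixes no lead comparison, so a reader of the results cannot tell from it which one the trial was sized for. Second, the plan promises 100% power for comparisons in general. An effect in SD units describes a continuous score. The same shift analysed as a yes/no status carries less information, so the power is lower and depends on how common the symptom is.

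**Working it through.** **Inputs.** From XI.2: 134 dyads per arm, 0.5 SD, alpha 0.05. The allocation is 1:1 (VII.E.2). The protocol does not state sidedness, so two-sided is assumed and one-sided is shown as a check. From section 1.6: "Prevalence of posttraumatic stress symptoms is estimated at 29% during the first month post-trauma and 13% between 3-6 months post-trauma". The same section gives 19% to 32% for PTSD within 12 months among adolescents hospitalized for injury. All four rates are background figures, used here as assumed comparison-arm rates.

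**Step 1: the plan's own figure, continuous score.** Power = Φ(d·√(n/2) − z), with d = 0.5 and n = 134.

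- 0.5 × √67 = 4.093.
- Two-sided: 4.093 − 1.960 = 2.133, and Φ(2.133) = 98.4% (98.3% with the t distribution).
- One-sided: 4.093 − 1.645 = 2.448, and Φ(2.448) = 99.3%.
- If all 300 dyads contribute (150 per arm): 0.5 × √75 = 4.330, and Φ(4.330 − 1.960) = 99.1%.

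The stated 100% is thus a generous rounding of 98%.

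**Step 2: the same shift analysed as symptomatic status.** Assume a normal score and a fixed cut-off that the proportion p1 exceeds in the Trauma Education arm. If Link lowers the score by 0.5 SD, its rate is p2 = 1 − Φ(z(1−p1) + 0.5). For p1 = 0.13, z = 1.126 and p2 = 1 − Φ(1.626) = 0.0519.

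Power of the uncorrected chi-square test = Φ[(p1 − p2 − 1.960·s0) / s1], where s0 = √(2·p̄(1−p̄)/n), s1 = √((p1(1−p1) + p2(1−p2))/n) and p̄ = (p1 + p2)/2. For p1 = 0.13: difference 0.0781, s0 = 0.0351, s1 = 0.0348, argument 0.265, power 60%.

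| Assumed Trauma Education rate | Background source (section 1.6) | Link rate after 0.5 SD shift | Power, 134 per arm |
|---|---|---|---|
| 13% | symptoms, 3-6 months | 5.2% | 60% |
| 19% | PTSD within 12 months, lower end | 8.4% | 71% |
| 29% | symptoms, first month | 14.6% | 82% |
| 32% | PTSD within 12 months, upper end | 16.7% | 84% |

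**Step 3: comparison.** One effect and one sample size give 98% or about 60% to 84%, depending on a choice that the protocol leaves open.

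**The case against.** The strongest reply is that the aim is openly exploratory. Such a trial may justify its size by a standardised effect for each comparison, and a standardised effect needs no named scale. Being in SD units, XI.2 can be read as covering scores only, and for a score 100% is close to 98%. Much of this stands. A reader might infer that 1.5 and XI.2 contradict each other. They do not: the fault is that no lead comparison is named and the power claim is worded too broadly. Even so, XI.2 does not limit itself to scores, and XI.1 plans status comparisons beside them.

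A reader might also infer that no result is protected from selection, or count scales, respondents and visits and quote a familywise error rate. The documents do not support this. Multiplicity control may be in the SAP, which is not shown, and the protocol sets out no such list of tests.

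The status figures are open to challenge too. The 29% is a first-month rate, whereas the first follow-up is at 6 weeks. The 13% comes from the literature, and the 19% to 32% covers a 12-month period. None is a planning rate, so the result is given only as a range.

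Finally, it would be wrong to say that access to mental health goes unmeasured because it is not among the seven scales. Section VII.E.6 says the follow-up questionnaire asks about mental health and community resources used.

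**Conclusion.** The point holds as a gap and an overbroad power claim. The protocol names no primary outcome, respondent or follow-up, and XI.2 attaches its power to an unnamed 0.5 SD difference.

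For a single continuous score the correct figure is 98% (two-sided 0.05, 134 per arm). The 2-point difference from 100% is small and would not alone justify a comment. The larger issue is that the figure does not extend to symptomatic status, where power is about 60% to 84%. That range assumes a normal score, a 0.5 SD shift, an uncorrected chi-square test and comparison-arm rates of 13% to 32%; other rates would give other figures. The point implies nothing about how the SAP handles multiplicity.

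**What to change.** Before outcome data are seen by arm, name one primary outcome in section 1.5: the scale, whether score or symptomatic status is analysed, the respondent, and the follow-up. The choice is the sponsor's. Restate XI.2 for that comparison. If it is a score, give 98% at 0.5 SD with two-sided alpha 0.05. If it is status, give the assumed comparison-arm rate and the power that follows. State that all other outcomes are hypothesis-generating unless the SAP controls multiplicity.

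If results by arm have already been seen, or no primary is wanted, say that the trial is hypothesis-generating and limit the figure in XI.2 to 98% for a single continuous score.

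The cost is a slightly less favourable power figure and fewer results that can be claimed as confirmed. No extra dyads are needed. If the sponsor chooses status and keeps the planned size, the lower power is simply reported.
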